# 9.3 Randomisation

Randomisation will be managed and carried out by LCTU. To ensure HV team clusters are evenly distributed, they will be randomly allocated either to the control or intervention group on a 1:1 basis, stratified by site.

Allocation of each HV Team cluster will be carried out when the first parent/carer's informed consent is obtained in each HV team.

The regular HV will be not be notified which group their HV team has been allocated at any point during the trial.

The researcher who has performed the consent with the parent/carer and subsequently completes all assessments, will also be blinded to the allocation of each cluster and will not know which allocation an individual participant belongs to.

Any unintended unblinding by the researcher will be recorded and another assessor will complete all further assessments for that participant. At each assessment, the outcomes assessor will be asked to guess the treatment allocation of the participant.

There will be a Research Administrator team member who will remain unblinded to the allocation and will be informed by LCTU of which of the two trial arms each HV team cluster has been allocated to and which HV team cluster subsequent participants belong to. This Research Administrator team member will be responsible for informing all participants after they have attended their baseline assessment, of their arm allocation within the trial. They will also be informed that they should not disclose the results of this allocation to the researcher who is performing the follow-up visits or their regular HV. SC trained HV will be informed if a new participant is enrolled into an intervention cluster and has requested CBT to enable delivery of the intervention. The SC Trained HV whilst not openly unblinded to cluster allocations, will be aware of those participants that require them to conduct intervention delivery.

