# 14.3 Statistical analysis plan

Statistical analyses will be undertaken according to a pre-trial Statistical Analysis Plan (SAP) written prior to database lock. Descriptive characteristics at baseline will be presented by treatment arm.

The LCTU Trial Statistician will be responsible for planning, monitoring and carrying out data analyses throughout the study, supervised by the LCTU Principal Statistician. The trial will be analysed and reported following the CONSORT statement for cluster RCTs.

The primary analysis will be performed using generalised estimating equations (GEE), which require a minimum of 40 clusters in order to produce reliable estimates. An Analysis of Covariance (ANCOVA) approach will be used with each participant's continuous EPDS score at 8 weeks follow-up as the outcome variable, adjusting for their EPDS at baseline and for the baseline cluster mean, with GEE to allow for differences between clusters. The model will also include a categorical variable for randomisation group and terms for the stratification

factors. The GEE model specification will include a log link function and a Gamma family distribution assumed for the outcome.

The primary analysis will analyse complete cases (i.e. missing data will not be replaced) and participants will be included in the group to which they were randomised irrespective of the intervention received. Secondary analyses will repeat the analysis on both an intention-to treat and per-protocol basis. Missing data will be imputed using multilevel multiple imputation methods in order to account for the clustered nature of the data.  Exploratory analyses of the primary outcome will investigate the effect of differing levels of compliance over and above the minimum level. Secondary outcomes will be analysed using a complete case population, in a similar manner to the primary outcome, modelled assuming an appropriate distribution family and link function. A sensitivity analysis of the primary outcome will adjust for ethnicity and social deprivation index at the individual level. Subgroup analyses of the primary outcome will be performed on the following factors: clusters participating in ICON, SC HV practitioner trained in CBT, social deprivation index and ethnicity.

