Analysis: Multiple imputation by chained equations will be used to deal with missing outcome and resource use values. The multiple imputation equation will include baseline variables showing a significant association with the trial outcomes alongside the pre-specified subgroups: clusters participating in ICON, SC HV practitioner trained in CBT, social deprivation index and ethnicity and their interaction terms. Subsequent analyses of imputed data will use the Rubin's rule to account for additional variability introduced into parameter values as a result of the imputation process.  Cost-effectiveness will be calculated as the mean cost difference between groups divided by the mean difference in outcomes (QALYs, parental depression, interruption-free nights) to give the incremental cost-effectiveness ratio (ICER) and (in the case of QALYs) incremental net monetary benefits (incremental NMBs). We will subject the results to extensive deterministic (one-, two- and multi-way) and probabilistic sensitivity analysis. For the latter, non-parametric methods for calculating the uncertainty around the mean cost and outcome differences will be ascertained using a non-parametric bootstrap.  The bootstrap replications will be used to construct cost-effectiveness acceptability curves, which will show the probability that each strategy is cost-effective for different values of the NHS' and society's cost-effectiveness for an additional unit of outcome.17 Likewise, the bootstrap replications will be used to calculate the 95% confidence interval around the mean NMBs and incremental NMB.

We will combine data on incremental costs with epidemiological data on projected numbers and undertake a budget impact analysis to evaluate what the total cost impact of rolling out the use of the SC package strategy would be were it to be scaled up. We will also use the probabilistic sensitivity analyses combined with the epidemiological information on projected numbers to undertake a value of information analysis to evaluate the potential economic value of future research on this topic.

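### Section 14.4 states no allowance for HV-team clustering in the economic imputation or bootstrap; applied at participant level, its intervals would be about 7.5% too narrow at the protocol's own ICC

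*Protocol*

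**What the plan says.** The unit of randomisation is the HV team. Section 9.3 says of the team clusters that "they will be randomly allocated either to the control or intervention group on a 1:1 basis, stratified by site".

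The clinical analysis in section 14.3 follows from that. The primary model is an ANCOVA "with GEE to allow for differences between clusters". For the analyses that use imputation, "Missing data will be imputed using multilevel multiple imputation methods in order to account for the clustered nature of the data".

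Section 14.4 sets its own methods for the economic analysis:

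- Missing data: "Multiple imputation by chained equations will be used to deal with missing outcome and resource use values".
- Content of the imputation model: "The multiple imputation equation will include baseline variables showing a significant association with the trial outcomes alongside the pre-specified subgroups: clusters participating in ICON", followed by the remaining subgroup factors and their interactions. Neither HV team nor trial arm is listed.
- Uncertainty: "the uncertainty around the mean cost and outcome differences will be ascertained using a non-parametric bootstrap". The resampling unit is not given.
- Use of the replications: "The bootstrap replications will be used to construct cost-effectiveness acceptability curves", and "the bootstrap replications will be used to calculate the 95% confidence interval around the mean NMBs and incremental NMB". The probabilistic sensitivity analysis, which is this bootstrap, also feeds the value-of-information analysis.

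Clusters appear in the analysis part of 14.4 only through the ICON subgroup factor. That factor varies between teams but does not identify the team.

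**The concern.** The two halves of one trial would treat the same clustering differently. EPDS at 8 weeks is the primary clinical outcome and also one of the economic outcomes. As written, its missing values would be imputed by a multilevel method in 14.3 and by chained equations with no listed team term in 14.4.

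A bootstrap that resamples parents treats members of one HV team as independent. If the ICC is above zero, the replications are then too tightly spread. The incremental NMB interval is too short, acceptability probabilities are pushed too far from 0.5, and the value of further research tends to be understated. Cost-effectiveness is part of both the research question and the hypothesis, so these outputs carry weight in the final report.

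**Working it through.** **Inputs.** From Protocol section 14.1: mean cluster size m = 4, CV of cluster size 0.625, ICC 0.037 for EPDS, with 0.01 and 0.05 as the protocol's sensitivity values. No ICC for costs, QALYs or NMB is given anywhere. I add 0.10 as an assumed upper case.

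**Reproducing the plan's design effect.**

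CV = (12 − 2)/4/4 = 0.625, using range/4 as the SD and the mean of 4.

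DE = 1 + [(1 + CV²)m − 1] × ICC = 1 + [(1.3906 × 4) − 1] × 0.037 = 1 + 4.5625 × 0.037 = 1.169. The plan states 1.17.

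280 × 1.17 = 327.6, i.e. 328; 328/4 = 82 clusters; adding 4 gives 86. These match the plan.

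**Effect of leaving clustering out.** If the standard error is computed as if participants were independent, it is too small by the factor 1/√DE. Then:

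- interval too narrow by 1 − 1/√DE;
- true coverage of a nominal 95% interval = 2Φ(1.96/√DE) − 1;
- an acceptability probability reported as 0.95 should be Φ(1.645/√DE).

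| ICC | Source | DE | Interval too narrow by | Coverage | Reported 0.95 becomes |
|---|---|---|---|---|---|
| 0.01 | 14.1 | 1.046 | 2.2% | 94.5% | 0.946 |
| 0.037 | 14.1 | 1.169 | 7.5% | 93.0% | 0.936 |
| 0.05 | 14.1 | 1.228 | 9.8% | 92.3% | 0.931 |
| 0.10 | assumed | 1.456 | 17.1% | 89.6% | 0.914 |

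**Simulation check.** The set-up was 41 clusters per arm, mean size about 4, CV about 0.625, a normal outcome, 1,500 trials and 400 resamples each. At ICC 0.037 the empirical SE was 0.119, the participant bootstrap gave 0.110 and the within-arm team bootstrap 0.117. Coverage was 92.0% for participants and 94.0% for teams. At ICC 0.10 coverage was 89.5% and 94.1%. A smaller comparison of 400 trials could not separate the two at ICC 0.037 (95.3% against 95.5%), as expected for a difference of this size.

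**Which resampling scheme.** Because randomisation is stratified by site, resampling teams within arm and site looks natural, but the cells are too small. With 86 teams, two arms and 8 to 10 sites, a cell holds 86/16 = 5.4 to 86/20 = 4.3 teams. Resampling n units shrinks the variance by (n − 1)/n, so the SE is too small by 1 − √(4.4/5.4) = 10% to 1 − √(3.3/4.3) = 12%. In simulation at ICC 0.037 with no site effect, arm-by-site resampling covered about 90–91%. The participant bootstrap covered about 92–93% and teams resampled within arm about 93–94%.

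**Not quantified.** The further effect of imputing without a team effect depends on the share of missing values (12% loss is planned for) and was not computed.

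**The case against.** The strongest reply is that 14.4 does not say what a reader might infer, namely single-level imputation and resampling of individual parents. Neither term appears. Chained equations can carry a team effect, a non-parametric bootstrap can resample teams, and the imputation variables are not said to be a complete list. Section 14.3 also commits the trial to the CONSORT statement for cluster trials, and a separate analysis plan may settle the detail. This stands to the extent that the understatement is conditional, not established.

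It does not remove the point. Section 14.4 is not a bare pointer to a later plan: it names its methods and the content of the imputation equation. The same protocol gives clustering as its reason for a different imputation method one section earlier. Side by side, the natural reading of 14.4 is the participant-level form.

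A reader might also infer that the true effect is large because service-use costs follow team practice and so have a higher ICC than EPDS. The documents do not support this. HV contacts head the resource list, but it also covers GP, midwife, A&E, outpatient and walk-in use. CBT is requested by the parent and delivered by a separately trained HV. QALYs come from the parent's own EQ-5D-5L. The 17% figure is therefore an assumption, at twice the highest ICC that the protocol considers.

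Finally, at ICC 0.037 the effect is modest. That also stands.

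**Conclusion.** The point holds in conditional form. Section 14.4 makes no stated allowance for HV-team clustering, which is inconsistent with 14.3. If its methods are applied at participant level, intervals are about 7.5% too narrow at ICC 0.037 and about 10% too narrow at ICC 0.05, with coverage of about 93% and 92%. At an assumed ICC of 0.10 they are about 17% too narrow, with coverage of about 90%. These figures rest on the protocol's cluster size and CV, and on applying EPDS ICCs to economic outcomes, for which none is given.

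It would be wrong to read this as a threat to the trial's main result. The primary clinical analysis, the sample size and the data collection are untouched, and no error in the point estimates of the ICER or incremental NMB has been shown. It should be corrected before the economic analysis is run, but it is not of the highest severity.

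**What to change.** Amend 14.4, or the health economics analysis plan with a reference from 14.4, to state:

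1. Missing costs and outcomes are imputed with the multilevel method of 14.3, with HV team as a random effect and trial arm in the imputation model.
2. Uncertainty comes either from a bootstrap that resamples whole HV teams within arm, not within arm-by-site cells, or from a bivariate multilevel or cluster-robust model of cost and outcome with site as a covariate.
3. The same replications or model estimates feed the NMB intervals, the acceptability curves and the value-of-information analysis.

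Reporting the observed ICCs for cost and QALY would show how much the allowance mattered.

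The cost is a change of wording and some extra programming. No new data are needed. The downside is slightly wider intervals.

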# 15 DATA MANAGEMENT

# 15.1 Data collection and source data identification

CRFs and participant reported outcome questionnaires will be the primary data collection instruments and treated as source data. All data requested in the CRFs should be recorded. All missing data will be followed up and resolved where possible. If the item is not applicable to the individual case, N/A will be written. All entries will be printed legibly in black ink, following ICH guidelines for Good Clinical Practice. All CRFs will be stored in a secure area with restricted access. Each enrolled participant will be allocated a unique Trial ID so that the CRFs and electronic database remains pseudonymised.

A copy of the participant consent form and information sheet will be placed in the health visitor notes and in the ISF.

Source Data is defined as the first place data is recorded, this will include:

- CRFs
- Participant completed questionnaires

#### 15.2 Data entry

Data entry will be conducted by the trial delivery team at site. Data collected from the source data as detailed above will be entered onto a validated web-based Remote Data Capture (RDC) system provided and managed by the LCTU. Access to the electronic CRF will be granted to authorized trial personnel only via a secure password-protected web-interface. The investigator and designated personnel must ensure accuracy, completeness and timeliness of data reported in the e-CRF and all required reports. Data reported on the e-CRF that are derived from source documents should be consistent with the source documents or the discrepancies should be explained. No identifiable data will be stored.

On-entry validation checks will be applied where required, and data entered will be checked for completeness, accuracy and timeliness by the trial team/trial manager/data manager, with queries managed using the data clarification functionality within the clinical data management system (CDMS) system. A Data Management Plan will be created with specific details on data handing and record keeping.

If trial data is required to be transferred electronically between the LCTU and the CI for the purposes of data management, this will be done in a secure manner. Information capable of identifying individuals will be held in a separate database with passwords restricted to the trial staff. Identifiable information will not be removed from the clinical centres or made available in any form to those outside the centre or the study.

#### **15.3** Data protection and participant confidentiality

Participants' personal data included in the study-related databases shall be treated in confidence and in compliance with ICH-GCP, the UK Policy Framework for Health and Social Care, the Data Protection Act 2018 and the EU General Data Protection Regulation (GDPR).

SC Protocol v5.0 30/06/2023

When processing or archiving personal data, the Sponsor or its representative shall take all appropriate measures to safeguard and prevent access to this data by any unauthorised third party.

Each participant will be assigned a unique identification number upon recruitment. The database will be password protected and only researchers collecting data will have access to this database. All personalised information for participants will be kept confidentially at the recruiting site unless there is specific consent and HRA approval for transfer of this to another site for study-related purposes.

Paper documentation will be stored in a locked filing cabinet in the relevant research office. Neither hard copies nor electronic files containing personal information will be removed from the research office or stored in a non-secure manner electronically. The trial research team will comply with the Data Protection Policy of the UoL and local NHS Trusts.

# **15.4** Data access and storage

All source data, trial documents and participant notes will be made available for monitoring, audits and inspections by the appropriate regulatory authorities, the Sponsor, NHS host organisations and LCTU.

All trial documentation will be retained in a secure location during the conduct of the study. Personal identifiable data will be retained for a maximum of 12 months following the end of the study, after which it will be destroyed, unless participants have expressed an interest in being invited to the results dissemination event and/or receiving a copy of the trial newsletter. In these circumstances, personal identifiable details such as names and contact details will be retained on a password protected database until required, and then destroyed.

All electronic data will be stored on secure network systems, to which only the relevant site and central trial research team staff have access. The secure networks are backed up daily by the University of Leicester IM&T.

For the purposes of this study, Nottingham Trent University, Leicester and University of Leicester will act as the joint Data Controller. University of Leicester will process data for analysis purposes.

#### 15.5 Archiving

Personal identifiable data generated by the trial will be retained for the minimum time determined by the regulatory authorities following the notification of the end of the trial before being destroyed in a confidential manner.

Following completion of the trial data analysis, data and essential trial records, including the final trial report, will be archived in a secure location for at least 15 years after the completion of the study, in accordance with LCTU SOPs. The data will be archived at a Sponsor approved archiving facility which will ensure that it is stored securely and accessed only by authorised

individuals. No study-related records, including hospital medical notes, will be destroyed unless or until the Sponsor gives authorisation to do so.

# 16 TRIAL ORGANISATION, REGULATION AND OVERSIGHT

#### **16.1** Ethical and regulatory considerations

Once Sponsor authorisation has been confirmed, the protocol, ICF, PIS and any proposed advertising material will be submitted to an appropriate Research Ethics Committee (REC), HRA, and host institution(s) for written approval. The trial will commence once all relevant approvals are in place and Sponsor 'Green Light' has been issued. Once Sponsor authorisation has been confirmed, the CI (or CI delegated team) will submit and, where necessary, obtain approval from all relevant regulatory authorities for all substantial amendments to the original approved documents. The only exception to this is when the change is necessary to eliminate urgent safety measures to the participants or when the change involves only logistical or administrative aspects of the trial when not meeting the requirements of non-substantial amendment submissions.

An annual progress report will be submitted to the REC within 30 days of the anniversary date on which the favourable opinion was given, and annually until the trial is declared ended. If the trial is ended prematurely, the CI will notify the REC, including the reasons for the premature termination. Otherwise, the CI (or delegate) will notify the REC of the end of the study. Within one year after the end of the study, the CI (or delegate) will submit a final report with the results, including any publications/abstracts, to the REC.

This trial will be conducted according in full conformity with the current revision of the Declaration of Helsinki (last amended October 2000, with additional footnotes added 2002 and 2004) and the UK Policy Framework for Health and Social Care Research (2017). It will also be conducted according to ICH GCP, relevant regulations and the SOPs and quality management procedures of Sponsor, host organisations and LCTU.

#### 16.2 Monitoring, audit and inspection

Nottingham Trent University, is the Sponsor of the study. The LCTU is responsible for the trial management and operates a risk-based Quality Management System, which will apply to this trial with quality checks and quality assurance audits performed as required.

As part of the quality management process, the trial will be subject to a risk assessment and a monitoring plan will be developed by the LCTU in accordance with the level of risk identified to participant safety, integrity of the trial and trial data validity. All trial monitoring will be conducted in accordance with the monitoring plan and will be undertaken by the LCTU. All monitoring will be performed by staff who are ICH/GCP trained and are competent in monitoring to all applicable regulatory guidelines. A documented monitoring log and audit trial will be maintained throughout the lifetime of the study.

#### 16.3 Trial registration

The SC trial will be registered on a recognised clinical trials database ISRCTN prior to recruitment commencing.

# **16.4** Insurance and indemnity

Nottingham Trent University holds an insurance policy to compensate trial participants for any study-related injury participating in the UK. The University's insurance cover routinely provides for negligent harm. If a patient is harmed due to negligence this would be covered by the Sponsor indemnity arrangements for all participants in clinical studies. If a trial participant wishes to make a complaint about any aspects of the way they have been treated or approached during the research project, the standard National Health Service complaint system will be available to them.

